6.1.2 DOSING AND ADMINISTRATION

Administration is as above – Coaching is combined with 6 times per week completion of tasks on mobile devices for a total of six weeks

6.2 PREPARATION/HANDLING/STORAGE/ACCOUNTABILITY

Leave blank. Text should be included under the relevant subheadings below.

6.2.1 ACQUISITION AND ACCOUNTABILITY

The software used to deliver iTEST is developed by NeuroUX a vendor that generates computer software. The software is web-based. See above for the flow of information through the portal.

6.2.2 FORMULATION, APPEARANCE, PACKAGING, AND LABELING

Not Applicable

6.2.3 PRODUCT STORAGE AND STABILITY

Not Applicable

6.2.4 PREPARATION

Not Applicable

6.3 MEASURES TO MINIMIZE BIAS: RANDOMIZATION AND BLINDING

There is no randomization and blinding is not possible in this study.

6.4 STUDY INTERVENTION COMPLIANCE

Adherence is assessed by calculating the ratio of completed iTEST training sessions out of the number possible (6x per week by 16 weeks = 96). Adherence is monitored by a dashboard available to the

research team. If a participant misses two consecutive training sessions (or one in the first week) they are called by the research assistants to troubleshoot adherence.

6.5 CONCOMITANT THERAPY

Concomitant treatment is allowed, and no restrictions are placed. Concomitant medication and other treatments address other aspects of schizophrenia do not impact introspective accuracy. Based on our review of the literature there is no intervention, either medication or behavioral, that has been shown to lead to improvement or a negative impact on introspective accuracy in schizophrenia (which is an impetus for the study). Therefore, there is no cause for our trial of iTEST to restrict concomitant medications. Other behavioral interventions are also permitted as again introspective accuracy is a novel mechanism and would not overlap with other behavioral interventions.

6.5.1 RESCUE MEDICINE

Not Applicable

7 STUDY INTERVENTION DISCONTINUATION AND PARTICIPANT DISCONTINUATION/WITHDRAWAL

Leave blank. Text should be included under the relevant subheadings below.

7.1 DISCONTINUATION OF STUDY INTERVENTION

Discontinuation from iTEST does not mean discontinuation from the study, and remaining study procedures should be completed as indicated by the study protocol. If a clinically significant finding is identified (including, but not limited to changes from baseline) after enrollment, the investigator or qualified designee will determine if any change in participant management is needed. Any new clinically relevant finding will be reported as an adverse event (AE).

7.2 PARTICIPANT DISCONTINUATION/WITHDRAWAL FROM THE STUDY

Participants are free to withdraw from participation in the study at any time upon request. An investigator may discontinue or withdraw a participant from the study for the following reasons:

- If any clinical adverse event (AE) or other medical condition or situation occurs such that continued participation in the study would not be in the best interest of the participant

The reason for participant discontinuation or withdrawal from the study will be recorded on the Case Report Form (CRF). Research participants who sign the informed consent form but do not receive the study intervention will not be replaced. Research participants who sign the informed consent form, and receive the study intervention, and subsequently withdraw, or are withdrawn or discontinued from the study, will not be replaced.

7.3 LOST TO FOLLOW-UP

A participant will be considered lost to follow-up if he or she fails to return for any of the follow up visits scheduled visits and is unable to be contacted by the study site staff.

The following actions must be taken if a participant fails to return to the clinic for a required study visit:

- The site will attempt to contact the participant and reschedule the missed visit within two weeks and counsel the participant on the importance of maintaining the assigned visit schedule and ascertain if the participant wishes to and/or should continue in the study.
- Before a participant is deemed lost to follow-up, the investigator or designee will make every effort to regain contact with the participant (where possible, 3 telephone calls and, if necessary, a letter to the participant's last known mailing address or local equivalent methods. These contact attempts will be documented in the participant's study file.
- Should the participant continue to be unreachable, he or she will be considered to have withdrawn from the study with a primary reason of lost to follow-up.

8 STUDY ASSESSMENTS AND PROCEDURES

8.1 EFFICACY ASSESSMENTS

Primary Targets: In addition to adherence, the primary Go/No Go targets of the R61 include both IA on trained (METER, VLMT) and untrained task (WCST). During each VLMT and Meter administration, participants are presented with 3 trials where lists of words or faces are presented. For the VLMT, immediately following each exposure to the list, participants were shown target and recognition foil words one-by-one and asked to indicate whether or not the word appeared on the list. For the METER task, participants are asked to guess the emotion in a picture of a human face from among anger, sadness, happiness, no emotion, or fear. After completion of the task, scoring includes the percentage of correct identifications of target words or faces per trial. In embedded validity tests, after each administration, participants self-reported if they were distracted or interrupted.

The reason that trained tasks are part of our Go/No Go criteria is because lack of improvement on trained tasks would call into question the ability of iTEST to modify IA, and would indicate need for program revisions. IA is calculated as the discrepancy (absolute) between each trial's correct performance from that estimated by the participant, which is nested within sessions and weeks. IA on the VLMT and METER tasks predict functional outcomes and is stable over time without training.

An additional Go/No Go component is transfer of training to an untrained task-based measure of IA, the Meta-Cognitive Wisconsin Card Sorting Test¹³. Wisconsin Card Sorting Task (WCST) (Heaton, Chelune, Talley, Kay & Curtiss, 1993). The WCST is a widely used measure of executive function that requires participants to match a presented card to one of four stimulus cards. There are several ways in which the card could be successfully sorted but participants are not informed of the criterion they should use to match the card. Instead, feedback is given after each sort (i.e. correct or incorrect), and participants must use this information to adjust their responses. After each sort, participants are asked to provide a judgement of correctness which are aggregated across sorts and used as the indicator of IA. IA on this task is also associated with functioning and improvement on this task would support that iTEST leads to

generalized improvement in IA. This adapted WCST was developed by Koren (2006)¹³ and modified by our group³³. The primary measure is the difference in accuracy judgments in relation to correctness³³. Notably, IA on the WCST is stable over repeat administrations. Further, were performance on the WCST to improve with repeated exposures, IA is disconnected from performance (see above) and models will adjust for performance.

8.2 SAFETY AND OTHER ASSESSMENTS

Baseline Assessment: At the baseline assessment, we will collect demographic and social contextual information (e.g., living situation) and we will gather medication data including sedation/sleepiness side effects via the Karolinska scale³⁴ at all assessment points. All participants will continue to receive their current treatments, as determined by their clinical providers throughout the study. We will also administer the Brief Assessment of Cognition in Schizophrenia-App Version (BACS)³⁵ and Virtual Reality Functional Capacity Assessment Tool³⁶ (VRFCAT) to assess global cognition and functional capacity, respectively, at baseline^{37,38}. In some past mobile interventions (with no coaching) adherence was poorer in patients with lower cognitive ability³⁹, so we will explore neurocognitive ability as a moderator. iTEST is designed to accommodate cognitive impairment by including device/app practice, a simplified guided user interface, and bi-weekly coaching. Finally, we will administer the Treatment Rationale Scale⁴⁰ to evaluate expectancies. Participants will receive 20 dollars for completing the screening portion of the baseline assessment and additional 30 dollars for completing the second part of the visit if eligible for a total of 50 dollars.

Symptom Assessments: Depression and psychotic symptoms will be assessed with the Calgary Depression Scale for Schizophrenia (CDSS)⁴¹ and Positive and Negative Syndrome Scale (PANSS)²⁶.

Table 3. Measures, Constructs, and Indicators		
Construct	Measure	Operational Indicator
Sample Characterization/Exploratory Moderators		
Cognition	BACS (Baseline only)	Total Score
Functional Capacity	VRFCAT (Baseline only)	Total Score
Psychotic Symptoms	PANSS Positive and Negative	Total Score
Depressive Symptoms	Calgary Depression Scale (CDSS)	Total Score
Treatment Expectancies	Treatment Rationale Scale	Total Score
Trained Task-Based IA Target (R61,R33)		
Trained Task-based IA	IA on METER and VLMT	Estimated vs Actual correct
Transfer of Training Target (R61, R33)		
Untrained Task-based IA	Metacognitive WCST	Global resolution score
Primary Outcome (R33; Exploratory in R61)		
Functional Outcome	Informant-Rated SLOF	Total Score
Secondary Outcomes		
Life space Mobility	GPS	Daily distance from home
Exploratory Mechanisms		
Strategy Use; Motivation and Defeatist Beliefs	Compensatory Cognitive Strategies Scale; CAINS Motivation, Defeatist Performance Beliefs	Total scores
Acceptability and Side Effects		
Intervention Satisfaction	Client Satisfaction Questionnaire (CSQ)	Total Score
User Engagement	Trials and Coaching Sessions Completed	% of Total Possible
Adverse Reactions	Negative Effects Questionnaire (NEQ)	Total Score

Primary Outcome: The informant-rated Specific Level of Function (SLOF) scale will be used to measure functional outcome¹⁵. The SLOF is a 43-item interview administered as informant- or self-report. The scale assesses the participant's current functioning integrated into a single higher-order factor¹⁶ integrating social, every day, and vocational activities. The SLOF emerged as the most reliable and externally valid scale-based measure of functioning in the team's prior validation study¹⁷. Informants ratings on the SLOF were also found to be sensitive to short term functional gains (12-24 weeks) in a treatment study conducted by [name]. We will also administer the self-rated version of the SLOF and calculate self-informant discrepancies in functioning. Greater discrepancies predicted worse functioning, and we will explore whether IA improvements on tasks result in increased convergence between self- and informant SLOF ratings. We considered additional EMA of function⁴², but decided not to due to the additional participant burden. See below for procedures related to informants. For completing all study visits and assessments, participants can earn up to \$340.

Exploratory Functional Outcome: As an additional objective digital biomarker of mobility pertinent to function (see^{43,44}), we will measure GPS lifespace, by way of Neurologger, an open-source application that records coordinates at a data rate of 1 sample/minute, yielding approximately 13K data points per person per week. Accuracy tolerance will be set at +/- 100 feet. Note that participants can opt out of this exploratory measure and still participate in the trial. As in our prior reports in which mobility was associated with community function^{43,44}, outcomes are median daily distance travelled from home and % of samples at home.

Exploratory Mechanistic Targets Linking Change in IA to Outcome: We will explore whether iTEST increases the use of strategies with the Compensatory Cognitive Strategies Scale (completed by informants and participants)⁴⁵ as well as motivation measured with Clinical Assessment Interview for Negative Symptoms (CAINS) Motivation and Pleasure (MAP) subscale⁴⁶. We will also explore Defeatist Performance Beliefs (DPAS)⁴⁷, which predict effort⁴⁸ and may improve with more accurate self-awareness of abilities.

Informant Ratings: We have attached to this protocol a standard script for recruitment of informants nominated by the participant. The script details the nature of the study and what is asked of the informant. The script is intended to be read over the phone to the participant and if willing, the questionnaires for informants (SLOF; Compensatory Cognitive Strategies Scale) are administered over the phone immediately thereafter (15-20 minutes). Informants then provide an address where a pay card can be sent. Informants are recruited at baseline and at follow up 16 weeks and receive 15 dollars per occasion for a total of 30 dollars.

Intervention Satisfaction: An adapted Client Satisfaction Questionnaire⁴⁹ keyed to both coaching sessions and mobile intervention components

For safety, we will administer the Columbia Suicide Severity Rating Scale⁵⁰. See suicide safety protocol. Since change in IA could theoretically lead to adverse experiences in some individuals (e.g., *greater awareness>depressed mood*), we will administer the Negative Effects Questionnaire (NEQ)⁵¹ at follow-ups. These are descriptive in nature.

We will also measure Clinical Worsening, which we define a criterion of a score of 96 on the PANSS Total Score or a 30% worsening from previous assessment. These criteria are linked to clinical global impression markers and are standard in acceptance. We will use the same approach as the Suicide

Safety Protocol to response to evidence or worsening as below:

Monitoring and Responding to Suicidal Ideation or Clinical Worsening During Lab-Visits Our safety monitoring protocol is standardized and details these procedures, how they are recorded, and what the staff, facility, and investigator responsibilities are. Whereupon participants endorse active suicidal ideation on the Columbia Suicide Severity Rating Scale (CSSRS ≥ 2 ; up to past 1 month) or recent suicidal behavior (past up to past 3 months), the investigators at the corresponding site will be contacted. Additionally, a score exceeding 96 on the PANSS total (severe symptoms) or 30% increase in symptoms from prior would also lead to contacting the investigator. Research staff will document recent treatment contacts and the resources available to participant, including whether or not their clinical providers are aware of the participants current status. The investigator (licensed provider) or delegated licensed provider will perform an in-person evaluation to determine if immediate emergency services are necessary. Also, at each study visit and particularly during our final assessment with participants we will provide resources lists and support linkage to available services, crisis lines, and other resources. These efforts will be critical in the final study visit in order to mitigate against any potential loss of benefit of contact with research staff that might be experienced after the conclusion of study participation. Participants who have completed the protocol and who are no longer in the study will be allowed to and encouraged to reach out to study investigators in case of questions about community resources pertinent to mental health care or suicide prevention. These plans are developed to be in full accordance with the NIMH's Guidance on Conducting Research with Persons at Elevated Risk for Suicide.

Monitoring or Responding to Suicidal Ideation during Remote or Mobile Device Interactions: We have taken several steps to ensure participant safety during the periods of remote assessment and interventions. All participants will be provided with staff contact information and emergency resources in a printed manual, and they will be instructed that they may call research staff at any time in case of questions or emergencies. Participants must provide release of information for our staff to contact their provider or key informant, so any emergent crises will be relayed to that participant's selected provider. Tile "shortcuts" are provided on the device home screen to resources (e.g., 24-hour Crisis Lines available in the region and to study staff). We, reporting to the Data and Safety Monitoring Board, will monitor these protocols during the course of the study and will make adjustments to study procedures should problems arise. We note that we are not directly querying about suicidal ideation or behavior on the device and so data elements entered by participants on the device are not specially linked to clinical responses. However, we will contact participants by telephone in case of lack of response, remote telephone coaching or check-in interactions with the study therapist will occur weekly, and we will conduct evaluations regarding potential crises upon contacting participants by phone using the same steps as outlined above in in-person contacts.

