1.3 SCHEDULE OF ACTIVITIES (SOA)

All activities listed will be administered on both sites.

	Screening Day -7 to -1	Baseline Day 0	Study Visit 2 Day 56 +/- 14 day	Study Visit 3 Day 84 +/- 14 day	Final Study Visit 4 Day 112 +/- 14 day
Procedures					
Informed consent	X				
SCID-5	X				
WRAT-4	X				
Demographics		X			
Medical history		X			
BACS		X			
VRFCAT		X			
MINI		X			
PSQI		X			
WHODAS 2.0		X			
PHQ-9		x			
PANSS		X	X	X	X
Calgary Depression Scale (CDSS)		X	X	X	X
Treatment Rationale Scale		X	X	X	X
CSSR-S		X	X	X	X
IA on METER and VLMT		X	X	X	X
Metacognitive WCST		X	X	X	X
Informant-Rated SLOF		X			X
GPS			X	X	X
Compensatory Cognitive Strategies Scale (Informant)		X			X
CAINS Motivation		X	X	X	X
Defeatist Performance Beliefs		X	X	X	X
Client Satisfaction Questionnaire (CSQ)		X	X	X	X
Negative Effects			X	X	X
Trials and Coaching Sessions Completed			X	X	X
HVLT			X	X	X
Metacog ER-40			X	X	X
Brief Regulation of Motivation Scale			X	X	X
Karolinska Sleepiness Scale			X	X	X
GAD-7			X	X	X

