4.1 OVERALL DESIGN

Hypothesis:

Target Engagement Hypothesis: Participants' adherence and average changes in IA for the mobile tasks and pre- post differences in meta-cognitive WCST will meet or exceed our go/no go criteria

Optimal Dosing: Target engagement may occur prior to 16 weeks, at week 8 or 12. We would select the optimal dose for the R33 is determined by selecting the earliest assessment point that reaches go/no go criteria - all participants receive the same dose

Phase of the trial, if applicable: This is a pilot behavioral intervention and so study phases are somewhat difficult to apply but would be mostly consistent with a Phase Ib study that is investigating acceptability and a preliminary effect in a diseased population

Design of Trial: Single arm, unblinded, open pilot trial.

Methods used to minimize bias: Measures are standardized and accepted endpoints and the sample has few exclusion criteria for entry

Dosing: All participants receive the same dose. We will investigate the point at which (among 8, 12, and 16 weeks) go/go criteria are met.

Intervention groups: This is a single arm trial and the duration of the intervention is 16 weeks.

Sites: There will be 2 sites – UCSD is the prime site and University of Texas at Dallas will be the secondary site with their own IRB.

Study Intervention: iTEST

Interim Analysis: No interim analysis is planned

Stratification: None

Name of sub-studies, if any, included in this protocol: None

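### GPS mobility, a named outcome, has no pre-training measurement in the Schedule of Activities, so this single-arm trial cannot estimate its change from baseline

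*Combined protocol and SAP*

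**What the plan says.** Section 4.1 describes the design as "Single arm, unblinded, open pilot trial". The Schedule of Activities (section 1.3) has five columns: Screening, "Baseline Day 0", and Visits 2, 3 and 4 at Days 56, 84 and 112.

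On GPS, section 8.2 states that "outcomes are median daily distance travelled from home and % of samples at home". Table 3 in the same section places GPS alone under its Secondary Outcomes heading, with the indicator "Daily distance from home". The text below the table calls it an exploratory functional outcome that participants may decline. In the schedule, GPS is marked at Visits 2, 3 and 4 only.

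On sleepiness, section 8.2, under its baseline-assessment paragraph, says that "we will gather medication data including sedation/sleepiness side effects via the Karolinska scale", and that this happens at every assessment point. The schedule row "Karolinska Sleepiness Scale" has no Baseline mark.

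On satisfaction, section 8.2 describes the CSQ as adapted to ask about the coaching and the mobile components. The schedule marks it at Baseline as well as at Visits 2 to 4.

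Four further rows (HVLT, Metacog ER-40, Brief Regulation of Motivation Scale, GAD-7) are also marked at Visits 2 to 4 only, for example "Metacog ER-40 X X X". They appear in the schedule and nowhere else.

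**The concern.** With no control arm, the contrast that speaks to an effect of training is after versus before. An outcome first recorded at Day 56 follows about eight weeks of training, and sections 3 and 4.1 expect that the go/no-go criteria may already be met by then. Follow-up values alone cannot show whether mobility rose, fell or stayed the same after training began. Section 8.2 presents GPS as an objective marker relevant to functioning, next to the informant-rated SLOF, so losing its pre-training comparison removes the objective counterpart to a rating scale. A missed baseline cannot be recovered once a participant has started training.

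The Karolinska and CSQ entries matter for a practical reason. Sites work from the schedule, so they would skip a baseline assessment that the text requires and would administer a satisfaction form about an intervention not yet received.

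**Working it through.** The plan gives no figure for this point, so the check is a comparison of passages, followed by an illustration.

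**Step 1: is the gap real or a shifted column?** Rows as printed in section 1.3:

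| Row | Baseline | Visit 2 | Visit 3 | Visit 4 |
|---|---|---|---|---|
| PANSS | X | X | X | X |
| Metacognitive WCST | X | X | X | X |
| Informant-rated SLOF | X | | | X |
| GPS | | X | X | X |
| Karolinska | | X | X | X |

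PANSS, WCST and SLOF keep their Baseline marks, so the blank GPS cell is not a column shift.

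**Step 2: sort the rows without a Baseline mark.** Eight rows are marked at Visits 2 to 4 only.
- Two need no baseline: Negative Effects (section 8.2 plans it at follow-ups) and sessions completed (a count that exists only after the start).
- One, Karolinska, is contradicted by section 8.2.
- That leaves 8 − 2 − 1 = 5 with no baseline anywhere: GPS, HVLT, Metacog ER-40, Brief Regulation of Motivation Scale and GAD-7.
- Of these five, only GPS is named as an outcome (Table 3 and section 8.2). The other four are absent from Table 3, section 3 and section 9.

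**Step 3: is a GPS baseline supplied elsewhere?** Section 8.2 gives the sampling rate and the metrics but no recording window. Section 6.1.1 (compensation) describes six days of mobile assessments at baseline and at weeks 9, 13 and 17; these mirror the training tasks, and GPS is not mentioned. Section 9 contains no GPS analysis, and section 9.4.9 is marked not applicable.

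**Step 4: what can still be estimated?** Write the mean at week *t* as m(t). Then

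m(16) − m(0) = [m(8) − m(0)] + [m(16) − m(8)].

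Only the second bracket is observed. If change is linear, its share is (16 − 8)/16 = 0.5. If change is complete by week 8, its share is 0.

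**Step 5: illustration of the loss.** Assumptions, not in the documents: a full 16-week change of d = 0.50, linear over time; equal SDs at each visit; correlation r between visits; two-sided 0.05. The sample sizes 60 and 48 come from section 9.2; GPS opt-out is ignored. The SD of change, in baseline SD units, is √(2(1 − r)), and power is approximately Φ(d√n / √(2(1 − r)) − 1.96). For n = 60 and r = 0.5 the SD of change is 1, so:
- from baseline: Φ(0.50 × 7.746 − 1.96) = Φ(1.91) = 0.97;
- week 8 to 16: Φ(0.25 × 7.746 − 1.96) = Φ(−0.02) = 0.49.

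| n | r | From baseline, d = 0.50 | Week 8 to 16, d = 0.25 |
|---|---|---|---|
| 60 | 0.3 | 0.91 | 0.37 |
| 60 | 0.5 | 0.97 | 0.49 |
| 60 | 0.7 | >0.99 | 0.71 |
| 48 | 0.3 | 0.83 | 0.31 |
| 48 | 0.5 | 0.93 | 0.41 |
| 48 | 0.7 | 0.99 | 0.61 |

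Section 9.4.1 sets significance testing aside, so these values show only how much information is lost. They are not the power of a planned test.

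**The case against.** **The GPS label is weaker than Table 3 suggests.** The table covers both award phases: the SLOF group above GPS is tagged as primary in the R33 and exploratory in the R61, while the Secondary Outcomes group carries no phase tag. The text of section 8.2 calls GPS exploratory and optional. The synopsis names the SLOF as the secondary endpoint, and section 3 names dosing. This stands, and it limits the weight of the point. It does not supply a baseline: section 8.2 still calls these metrics outcomes.

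**GPS is passive and continuous.** A mark at Visit 2 could mean collecting data recorded since onboarding. That is possible, because the recording window is not stated. But no passage provides for a pre-training period, and section 6.1.1 starts daily training the day after the initial session. The plan needs to say when recording begins.

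**Stronger readings.** A reader might infer that no change at all can be estimated. That is not so: weeks 8, 12 and 16 give repeated measures, and only change from before training is lost.

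A reader might also count six failed outcomes and multiply up to 6 × 3 × 60 = 1,080 wasted measurements. The documents do not support this. Four of the six have no stated outcome role or analysis, Karolinska is a conflict between text and schedule, and the count ignores GPS opt-out and the 20% attrition scenario. It also measures no harm to a planned inference.

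Nor is the baseline-only PHQ-9 an error, since the CDSS follows depression at every visit.

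**Conclusion.** The point holds for GPS. If the schedule is followed as written, change in GPS mobility from before training cannot be estimated, and the remaining week 8 to 16 contrast misses whatever was reached by week 8: half of a linear change, or all of a change complete by then. Those shares rest on assumed time courses, and the power figures also on assumed correlations.

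Two schedule errors stand beside it: the missing Karolinska baseline, which conflicts with section 8.2, and the CSQ at baseline. The four schedule-only measures raise a question of purpose and are not a demonstrated defect.

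A reader might infer that the go/no-go decision is compromised. It is not: IA on VLMT and METER, the metacognitive WCST and the informant-rated SLOF all have Baseline marks, and adherence needs none. This should be corrected before enrolment, but it does not threaten the primary purpose of the trial.

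**What to change.** - Add a Baseline mark for GPS in section 1.3. Collect it passively during the existing six-day baseline mobile-assessment week, state that this week ends before training starts, give the recording window for each later assessment, and report GPS as change from that baseline.
- Use one label for GPS, secondary or exploratory, in Table 3 and the text, and say which award phase it applies to.
- Add the Baseline Karolinska mark so that the schedule agrees with section 8.2.
- Remove the Baseline CSQ mark. Expectancy before treatment is already covered by the Treatment Rationale Scale.
- For HVLT, Metacog ER-40, Brief Regulation of Motivation Scale and GAD-7, state the purpose. Add a Baseline mark for any that is meant to show change; otherwise describe it as follow-up description only.

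The cost is an edit to the schedule and slightly more baseline burden, partly offset by dropping the CSQ there. GPS adds no testing time, and participants can still opt out.

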8.3.4 TIME PERIOD AND FREQUENCY FOR EVENT ASSESSMENT AND FOLLOW-UP

The occurrence of an adverse event (AE) or serious adverse event (SAE) may come to the attention of study personnel during study visits and interviews of a study participant.

All AEs including local and systemic reactions not meeting the criteria for SAEs will be captured on the appropriate case report form (CRF). Information to be collected includes event description, time of onset, clinician's assessment of severity, relationship to study product (assessed only by those with the training and authority to make a diagnosis), and time of resolution/stabilization of the event. All AEs occurring while on study must be documented appropriately regardless of relationship. All AEs will be followed to adequate resolution.

Changes in the severity of an AE will be documented to allow an assessment of the duration of the event at each level of severity to be performed. AEs characterized as intermittent require documentation of onset and duration of each episode.

Research staff will record all reportable events with start dates occurring any time after informed consent is obtained until 7 (for non-serious AEs) or 30 days (for SAEs) after the last day of study participation. At each study visit, the investigator will inquire about the occurrence of AE/SAEs since the last visit. Events will be followed for outcome information until resolution or stabilization.]

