8.3.5 ADVERSE EVENT REPORTING

Adverse Event Definitions and Protocol: Any AE that is reported by the participant is noted by a study team member and will be reported to the PI and to the UCSD (or UTD or UM) Human Research Protection Office (HRPP) per their reporting policy and procedures. Any additional follow-up evaluations required by the event will also be evaluated by the PI and sent to HRPP per their reporting policy as well as to the DSMB. Any participant who develops an SAE will be followed-up through the resolution of the event and for one month thereafter. A log is kept of all AEs in a secure location at UCSD. Trained

research personnel will assess for any serious medical or psychological conditions that may require immediate medical attention or psychiatric treatment. Should attention be required, staff will provide these individuals with information about suitable referrals, including local hospitals, clinics, and/or relevant health-care and mental health professionals, and they the PIs will strongly encourage the individuals to follow up with these referrals. SAEs are reported to the DSMB, NIMH, and the HRPP within 24 hours

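### From Visit 3 the Clinical Worsening rule has no comparison with baseline, so a gradual PANSS rise of 30% or more does not trigger the automatic in-person evaluation

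*Combined protocol and SAP*

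**What the plan says.** Section 8.2 states the rule twice. The definition is "a criterion of a score of 96 on the PANSS Total Score or a 30% worsening from previous assessment". The operational paragraph on lab visits says that "a score exceeding 96 on the PANSS total (severe symptoms) or 30% increase in symptoms from prior would also lead to contacting the investigator". The consequence is that the investigator or a delegated licensed provider "will perform an in-person evaluation to determine if immediate emergency services are necessary".

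The Schedule of Activities (Section 1.3) marks PANSS at baseline (Day 0), at "Study Visit 2 Day 56 +/- 14 day", at Visit 3 (Day 84) and at Visit 4 (Day 112). Section 5.1 also lists a PANSS among the screening measures. Section 5.2 limits entry on the P2 item only, not on the total.

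Other routes by which worsening could come to attention are:
- Section 7.1: a clinically significant finding, which may be a change from baseline, leads the investigator or a designee to decide on management, and a new relevant finding is reported as an adverse event.
- Section 8.2, on remote contact: weekly telephone coaching or check-ins.
- Section 8.3.3.2: the examining clinician assesses each adverse event for its relationship to the intervention.
- Section 8.3.4: "At each study visit, the investigator will inquire about the occurrence of AE/SAEs since the last visit".
- Section 8.3.5: "Any AE that is reported by the participant is noted by a study team member and will be reported to the PI".

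**The concern.** The relative limb uses a moving comparator. At Visit 2 it is the baseline; at Visits 3 and 4 it is the visit before. Several rises, each well short of 30%, can add up to more than 30% since study entry without any one of them meeting the rule, as long as the total stays below the level limb.

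The rule can also treat the same deterioration differently according to attendance. Take a participant at 60 at baseline and 79 at Visit 3. If Visit 2 was missed, the previous assessment is the baseline and the rule fires (79/60 = 1.317). If Visit 2 was attended with a score of 68, the steps are 13.3% and 16.2%, and it does not fire.

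At stake is the one evaluation that a PANSS change makes obligatory. A participant whose total has risen by about a third since entry may not receive it unless staff act on an adverse event or on judgement. No go/no-go criterion uses PANSS, and depression, suicidality and negative effects have their own instruments.

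**Working it through.** **Inputs.** Relative limb: 30% from the previous assessment. Level limb: 96, or above 96 (Section 8.2 has both). PANSS at baseline and three follow-ups (Section 1.3). The plan gives no figure to reproduce. It also does not say how the percentage is computed, so two conventions are tried: the raw total, which is the plain reading, and the total minus 30. The value 30 as the scale minimum is an assumption; the documents do not give it.

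**Rule as coded.** Flag at a visit if the score is over the cap (95 for the 96-or-more reading, 96 for the above-96 reading), or if (current − previous) ≥ 0.30 × previous. On the second convention, replace previous by (previous − 30) on the right-hand side.

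**Visit 2.** The comparator is the baseline, so no rise of 30% or more from baseline can be missed.

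**Lead example, 60, 66, 72, 79**
- Raw: 66/60 = 1.100, 72/66 = 1.091, 79/72 = 1.097. From baseline 79/60 = 1.317, or +31.7%. Never flagged.
- Minus 30: 36/30 = 1.200, 42/36 = 1.167, 49/42 = 1.167. From baseline 49/30 = 1.633, or +63.3%. Never flagged.

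**Second example, 60, 68, 79, 93**
- Raw: 1.133, 1.162, 1.177. From baseline +31.7% at Visit 3 and +55.0% at Visit 4. Never flagged.
- Minus 30: 38/30 = 1.267, 49/38 = 1.289, 63/49 = 1.286. Never flagged.

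**Smallest equal steps that add up to 30%.** Two steps: 1.30^(1/2) = 1.140, about 14% each. Three steps: 1.30^(1/3) = 1.091, about 9% each.

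**Baselines with a gap** (whole points from 31 up, all paths enumerated, same result under either cap)
- Raw: up to 73. Check: 95/1.3 = 73.1 and 96/1.3 = 73.8. From 74 upward a 30% rise is caught by the level limb.
- Minus 30: 34 to 80. Check at the top: 65/1.3 + 30 = 80.0 and 66/1.3 + 30 = 80.8.
- A raw rise of 30% or more that escapes both conventions: 44 to 73.

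**Largest unflagged raw rise by Visit 4, cap 95**

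| Baseline | Raw rule: path | Rise | Minus-30 rule: path | Rise |
|---|---|---|---|---|
| 45 | 45, 58, 75, 95 | +111% | 45, 49, 54, 61 | +36% |
| 50 | 50, 64, 83, 95 | +90% | 50, 55, 62, 71 | +42% |
| 60 | 60, 77, 95, 95 | +58% | 60, 68, 79, 93 | +55% |
| 70 | 70, 90, 95, 95 | +36% | 70, 81, 95, 95 | +36% |

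These are upper bounds. They need steps just under 30% or a rise to the cap, and they do not describe what is likely.

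**Effect of a baseline limb on the raw total.** The lead example is flagged at Visit 4. The second is flagged first at Visit 3. A limb that fires at every visit would also flag 60, 80, 79, 78 three times (+33.3%, +31.7%, +30.0% from baseline), although that participant is evaluated at Visit 2 under the present rule and then improves. Restricting the limb to the first time it is reached brings this back to one flag.

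**The case against.** The strongest reply is that the rule is meant for acute triage. Its stated consequence is an evaluation of whether emergency services are needed at once, and for that purpose recent change or a high absolute level is a coherent test. Section 8.2 adds that the criteria are tied to global impression markers and are standard. This stands as a reason to keep both limbs. It does not explain why the comparator is the baseline at Visit 2 and something else later.

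The second reply is that slow worsening has other routes. Section 7.1 mentions changes from baseline, adverse events are asked about at each visit and assessed by a clinician, and there is weekly telephone contact. This also stands, and it narrows the gap. None of these routes has a PANSS threshold, however, and none makes an evaluation obligatory on a PANSS change.

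Third, the size is hypothetical. Entry requires two months of stable treatment, and no baseline distribution is given. That is correct, and no frequency is claimed here.

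Two wording matters are lesser. The definition and the operational paragraph ("a score exceeding 96 on the PANSS total (severe symptoms) or 30% increase in symptoms from prior") disagree at a score of exactly 96, which is a real inconsistency at one value. How the percentage is computed may be set in the standardized safety monitoring procedure that Section 8.2 mentions, so its absence here is a missing detail at most.

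**Conclusion.** The gap holds as a narrow point: at Visits 3 and 4 no PANSS change from baseline obliges the evaluation, and a gradual rise of 30% or more can miss it under either cap and either way of computing the percentage. On the raw total it concerns baselines up to 73. The range of 34 to 80 for the other convention rests on the assumed minimum of 30. Severity is minor, and the change is a cheap improvement.

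A reader might infer that slowly worsening participants go unmonitored, that many would be missed, or that the present rule is unsuitable. The documents do not support these readings: other routes exist, the frequency cannot be estimated, and both limbs suit acute triage. Nor does the point touch the go/no-go decision. Confidence is high in the arithmetic and in the reading of the comparator. Whether the rule should also cover gradual worsening is a design judgement, and it favours the change because the data are already collected.

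**What to change.** In both places in Section 8.2:

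1. Keep the two present limbs for acute triage.
2. Add a third: *or a rise of at least 30% in the raw PANSS total from the Day 0 baseline, the first time this is reached, unless the participant has already been evaluated under this rule and has not worsened since.* Naming Day 0 avoids doubt about the screening PANSS, and naming the raw total settles the computation for this limb.
3. Write the level limb as *96 or more* in both places.

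**Cost.** Wording only; PANSS is already scheduled at all four visits. At Visit 2 the new limb repeats the present one. At Visits 3 and 4 it may bring a few more investigator contacts and licensed-provider evaluations, and the first-occurrence wording limits these. On the raw total a baseline of 60 needs a rise of 18 points (0.30 × 60) to trigger.
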